10.1 EVALUATING AES AND SAES

10.1.1 ASSESSMENT OF INTENSITY

The Investigator will make an assessment of intensity for each AE and SAE reported during the study. The assessment will be based on the Investigator's clinical judgement. The intensity of each AE and SAE recorded in the eCRF should be assigned to one of the following categories:

- Mild; An event that is easily tolerated by the participant, causing minimal discomfort and not interfering with everyday activities
- Moderate; An event that is sufficiently discomforting to interfere with normal everyday activities
- Severe; An event, which is incapacitating and prevents normal everyday activities

An AE that is assessed as severe should not be confused with an SAE. Severity is a category utilised for rating the intensity of an event; and both AEs and SAEs can be assessed as severe.

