6.7 LABORATORY DATA

All tests listed below will be performed as per the time points indicated in the participant timeline in section Table 1 (Section 2, Study Design). In addition, laboratory safety tests may be performed at unscheduled times, if deemed necessary by the investigator and abnormal results recorded as an adverse event if clinically significant. Trial sites will use the routine local laboratories. If samples are requested elsewhere (eg via a community based doctor) the laboratory results report should be requested. Results must be reviewed and signed by a physician, the local PI is responsible for ensuring appropriate documentation. After consent is obtained, clinically significant abnormal laboratory results will be recorded in the adverse events log. Individual result values will not be transcribed to the eCRF unless outside the normal range.

Blood samples for methotrexate polyglutamate and filaggrin analysis will be sent to the KCL 9th floor St John's Institute of Dermatology Laboratory, Guy's Hospital, for processing – see sample flow diagrams (Appendix 7) and lab manual for logistical arrangements and sample analysis plans. Where optional consent is provided by participants, there will be long term storage of DNA samples in the

St John's Research Tissue Bank (part of Guy's Research Tissue Bank, Ethics Committee ref: 07/H10712/106; HTA License Number 12521).

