1.2.1.1 RENAL IMPAIRMENT

Renal impariment is a frequent and potentially serious complication that can occur during ciclosporin therapy. These functional changes are dose-dependent and are initially reversible, usually responding to dose reduction. During long-term treatment, some patients may develop structural changes in the kidney (e.g. interstitial fibrosis).

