1.4.2.2 SAFETY BLOODS

The following safety bloods will be performed at weeks 4, 13, 26, 39 and 52:

HAEMATOLOGY Haemoglobin Haematocrit Total and differential leukocyte count Red blood cell count Platelet count

BIOCHEMISTRY

Creatinine Potassium Liver function tests (LFTs) Lipids

Note: specific thresholds at which drug interruption is suggested can be found in the SmPC.

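### The AE intensity scale has no criterion that fits laboratory findings, although clinically significant ones are logged and graded as AEs

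*Protocol*

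**What the plan says.** Protocol section 10.1.1 asks the investigator to judge the intensity of each AE and SAE and to assign one of three categories:

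- The lowest category is worded "Mild; An event that is easily tolerated by the participant, causing minimal discomfort and not interfering with everyday activities".
- The middle category is for events uncomfortable enough to get in the way of ordinary life.
- The highest category is worded "Severe; An event, which is incapacitating and prevents normal everyday activities".

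The grade is left to clinical judgement, and the section warns that a severe event is not the same thing as a serious one.

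Section 6.5.3 lists severity among the items recorded for every AE. Section 6.7 states that after consent "clinically significant abnormal laboratory results will be recorded in the adverse events log". It adds that "Individual result values will not be transcribed to the eCRF unless outside the normal range", so out-of-range values are held in the database. Sites use their own local laboratories.

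The drug appendices name harms that are found by blood test. Appendix 1 (1.2.1.1) describes renal impairment as "a frequent and potentially serious complication that can occur during ciclosporin therapy".

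**The concern.** The grading rule and the contents of the AE log do not match. A raised creatinine, an abnormal liver test or a low blood count can be clinically important while the participant feels nothing and lives normally. The three definitions ask only what the participant feels and can do, so they offer no basis for separating a small abnormality from a large one.

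This touches secondary objective 3 (safety and tolerability against standard of care), the AE safety outcomes in section 4.2, and the AE reporting to the DMC in section 10.3. Severity also enters the definitions of expectedness in section 10.1.3. The enhanced capture for AEs of special interest (section 10.2) does not fill the gap, because it covers eye disease, joint pain and facial rashes, all of which are felt or visible.

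This is not a detail that can be left to the SAP. The grade is assigned at site under the protocol's definitions, and an analysis plan cannot correct it afterwards, although it can add value-based reporting beside it.

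**Working it through.** The protocol gives no figure to reproduce. The check is a side-by-side reading plus a count of scheduled tests.

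**Step 1: apply the definitions to a symptom-free laboratory AE.**
- Mild needs good tolerance, minimal discomfort and no interference with activities: satisfied.
- Moderate needs discomfort enough to interfere with activities: not satisfied.
- Severe needs incapacity: not satisfied.

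By the wording, only mild fits, and the laboratory value plays no part.

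**Step 2: look for a value-based criterion elsewhere.**
- Section 6.7 sets the rule for entering a laboratory result in the AE log (clinical significance), not a rule for grading it.
- Section 10.2 contains no laboratory item.
- Appendix 4 (1.4.2.2) notes that "specific thresholds at which drug interruption is suggested can be found in the SmPC". That pointer concerns interruption of treatment, not the intensity grade.

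No section grades laboratory AEs by value.

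**Step 3: allow for clinical judgement.** Judgement selects among the three categories but is given no laboratory anchor. An investigator either follows the wording and records mild, or departs from it by a personal rule. There are 36 centres (section 5.1), and principal investigators and other site staff, apart from the outcome assessors, know the allocation (section 8.4, Table 2). The supportable expectation is a mixture of under-grading and inconsistent grading.

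**Step 4: count the scheduled post-baseline safety bloods**, for participants who stay on the allocated drug, before any dose-increase extras:

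| Arm | Weeks | Count |
|---|---|---|
| Ciclosporin (App. 1, 1.4.2.3) | 2, 4, 6, 8, 13, 26, 39, 52 | 8 |
| Methotrexate (App. 2, 1.4.3.2) | 2, 4, 13, 26, 39, 52 | 6 |
| Abrocitinib (App. 4, 1.4.2.2) | 4, 13, 26, 39, 52 | 5 |
| Dupilumab (App. 3, 1.4.2.2) | 13, 26, 52 | 3 |

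For abrocitinib, the schedule of events in Appendix 4 and the week 39 footnote to Table 1 leave out week 39, which gives 4. The two need reconciling, but the ordering of the arms is the same either way. Ciclosporin, the control in every comparison, has 8/3 ≈ 2.7 times as many scheduled tests as dupilumab.

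**Step 5: what follows.** The chance of detecting a silent abnormality, and so of creating a laboratory AE, differs by arm. A misfit in grading laboratory AEs therefore falls unevenly on any table of AEs by severity. Computing the size or direction would need the rate of laboratory AEs by arm and the grades investigators give them. The protocol has neither.

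**The case against.** The strongest reply has four parts.

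**Judgement.** Section 10.1.1 bases the grade on clinical judgement, so a reader should not infer that every silent toxicity will be recorded as mild whatever its value. This stands: that outcome is the literal reading, not a prediction. It does not cure the defect, because judgement without an anchor does not give comparable grades.

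**No stated severity comparison.** A reader might infer that a planned between-arm comparison of severity is distorted. The protocol specifies none. Section 4.2 lists AEs and AEs of special interest, section 3.2 gives a general safety objective, and section 10.3 says only that relevant AEs go to the DMC. This also stands, so the point is a risk to any severity table that is produced.

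**Other routes.** Important medical events count as serious whatever their intensity (section 10). The AE log records impact on treatment and outcome (6.5.3). Dose changes and reasons (6.5.5), discontinuations (6.8.1) and reasons for stopping (7.3) are captured, and out-of-range values are kept (6.7). Important toxicity is therefore not lost. What remains unreliable is the intensity field itself.

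**Silent versus felt harms.** It is tempting to say that harms of the other three drugs are silent and those of dupilumab felt, so that the scale favours the comparators over dupilumab. The lists of common effects do not support this. By my classification, about 16 of 24 for ciclosporin are felt or visible; only 3 of 16 for methotrexate are blood counts; 8 of 9 for abrocitinib are symptomatic or visible; and dupilumab's list includes eosinophilia, a laboratory finding. No direction of bias can be claimed.

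The entry rule is also narrower than it may look: current section 6.7 logs only clinically significant abnormalities.

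**Conclusion.** The concern holds in a limited form. Section 10.1.1 fixes an intensity scale that does not fit one class of event the protocol requires to be graded on it. The literal reading gives mild for any symptom-free laboratory abnormality, and the practical result is likely to be inconsistent grading. Tables of AEs by severity are at risk of understating laboratory toxicity, unevenly across arms that have 8, 6, 5 and 3 scheduled safety bloods.

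The conclusion rests on the wording of sections 10.1.1, 6.7 and 6.5.3, on the absence of a value-based criterion elsewhere in the protocol, and on the assumption that severity will be tabulated in some form. It does not rest on assumed event rates, and none would establish a size. A distorted safety comparison or a reversed ranking of drugs is not shown. The defect is moderate and inexpensive to correct.

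**What to change.** 1. In section 10.1.1, state that AEs that are laboratory findings are graded by value on a named, published numerical scale, with its grades mapped to mild, moderate and severe. Assign the grade at AE entry from the local laboratory report and its reference range. Deriving it only centrally is not assured, because in-range values are not transcribed, laboratories are local, and section 6.7 does not say that reference ranges are held.
2. Keep the functional definitions for symptomatic events, and take the higher grade where both apply.
3. Report the out-of-range laboratory values already in the eCRF by value and by arm beside the AE severity table, in DMC and final reports, and note the different testing frequency.
4. Regrade laboratory AEs already logged where the recorded value and range allow, and say how many could not be regraded.

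The cost is a short amendment, brief site guidance, some programming and a limited one-off regrade, with no new tests. The downside is two grading rules in one AE log. The change affects recording and reporting only, not dosing or clinical management.

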10.1.2 ASSESSMENT OF CAUSALITY

The Investigator is obligated to assess the relationship between investigational product and the occurrence of each AE/SAE. The Investigator will use clinical judgment to determine the relationship. Alternative causes, such as natural history of the underlying diseases, concomitant therapy, other risk factors, and the temporal relationship of the event to the investigational product will be considered and investigated.

The causal relationship to the study product assessed by the Investigator (or medically qualified delegate) should be assessed using the following classifications:

- Not Related: In the Investigator's opinion, there is not a causal relationship between the study product and the AE.
- Unlikely: The temporal association between the AE and study product is such that the study product is not likely to have any reasonable association with the AE.
- Possible: The AE could have been caused by the study participant's clinical state or the study product.
- Likely: The AE follows a reasonable temporal sequence from the time of study product administration, abates upon discontinuation of the study product and cannot be reasonably explained by the known characteristics of the study participant's clinical state.
- Definitely: The AE follows a reasonable temporal sequence from the time of study product administration or reappears when study product is reintroduced.

There may be situations when an SAE has occurred, and the Investigator has minimal information to include in the initial report to the Sponsor. However, it is very important that the report is submitted within 24 hours of becoming aware of the event. The Investigator must always attempt to assess causality for every event prior to transmission of the SAE form to the Sponsor, however the initial report should be sent without this information if needed to meet reporting timelines. The Investigator may change his/her opinion of causality considering follow-up information, documenting this on an SAE follow up form and sending to the sponsor accordingly. The causality assessment is one of the criteria used when determining regulatory reporting requirements.

10.1.3 ASSESSMENT OF EXPECTEDNESS

A reasonable possibility of a relationship conveys that there are facts, evidence and/or arguments to suggest a causal relationship, rather than a relationship that cannot be ruled out.

- Expected: An adverse reaction, the nature or severity of which is consistent with the applicable Reference Safety Information (RSI) in the Summary of Product Characteristics for an approved medicinal product
- Unexpected: An adverse reaction, the nature or severity of which is not consistent with information in the relevant reference document.

Section 4.8 of the SmPC's will form the RSI for the IMPs in this trial. Please refer to the drug-specific appendices 1-4 for the SmPC versions currently approved as the RSI for assessing expectedness.

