10 ADVERSE EVENT MANAGEMENT AND REPORTING

All adverse events will be recorded from consent to the end of study visits in the participants medical notes, the AE source data worksheets and the eCRF. SAE's will be additionally reported, within 24 hours of site becoming aware of the event, to the KHP-CTO.

All SAEs, SARs and SUSARs will be reported immediately (and certainly no later than 24hrs) by the Investigator to the KHP-CTO for review in accordance with the current Pharmacovigilance Policy and as per the instructions on the SAE report form.

The Medicines for Human Use (Clinical Trials) Regulations 2004 and Amended Regulations 2006 gives the following definitions:

- Adverse Event (AE): Any untoward medical occurrence in a participant to whom a medicinal product has been administered, including occurrences which are not necessarily caused by or related to that product.
- Adverse Reaction (AR): Any untoward and unintended response in a participant to an investigational medicinal product which is related to any dose administered to that participant.
- Unexpected Adverse Reaction (UAR): An adverse reaction the nature and severity of which is not consistent with the information about the medicinal product in question set out in the summary of product characteristics (SmPC) for that product.
- Serious adverse Event (SAE), Serious Adverse Reaction (SAR) or Suspected Unexpected Serious Adverse Reaction (SUSAR): Any adverse event, adverse reaction or unexpected adverse reaction, respectively, that:
 - results in death
 - is life-threatening
 - required hospitalisation or prolongation of existing hospitalisation (excluding elective or planned procedures)
 - results in persistent or significant disability or incapacity
 - consists of a congenital anomaly or birth defect
- Important Medical Events (IME) & Pregnancy: Events that may not be immediately lifethreatening or result in death or hospitalisation but may jeopardise the participant or may require intervention to prevent one of the other outcomes listed in the definition above should also be considered serious. Although not a serious adverse event, any unplanned pregnancy will also

be reported via the SAE reporting system.

• Adverse Event of Special Interest (AESI): Pre-specified adverse events of interest for which more detailed information will be collected

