10.3 ADVERSE EVENT PROCESSING RESPONSIBILITIES

The Sponsor has delegated the delivery of the Sponsor's responsibility for Pharmacovigilance (as defined in Regulation 5 of the Medicines for Human Use (Clinical Trials) Regulations 2004) to the KHP-CTO.

The KHP-CTO will report SUSARs to the relevant ethics committee and to the MHRA. Reporting timelines are as follows:

- SUSARs which are fatal or life-threatening must be reported not later than 7 days after the sponsor is first aware of the reaction. Any additional relevant information must be reported within a further 8 days;
- SUSARs that are not fatal or life-threatening must be reported within 15 days of the sponsor first becoming aware of the reaction.

The Chief Investigator and King's Health Partners Clinical Trials Office (KHP-CTO) (on behalf of the co-sponsors) will submit a Development Safety Update Report (DSUR) relating to this trial IMP, to the MHRA and REC annually.

The Trial Statistician will report relevant adverse events to the Data Monitoring Committee.

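### Section 10.1.3 classes a listed reaction of greater than listed severity as both expected and unexpected, leaving its SUSAR status open; separately, 'Definitely' related asks for less than 'Likely'

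*Protocol*

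**What the plan says.** **Expectedness.** Protocol section 10.1.3 has two bullets. The first reads "Expected: An adverse reaction, the nature or severity of which is consistent with the applicable Reference Safety Information (RSI". The second reads "Unexpected: An adverse reaction, the nature or severity of which is not consistent with information in the relevant reference document". The RSI is section 4.8 of each product's SmPC. Section 10, in a list of definitions attributed to the UK clinical trials regulations, describes an unexpected adverse reaction as "An adverse reaction the nature and severity of which is not consistent with the information about the medicinal product in question", and builds the SUSAR definition on that term plus a seriousness criterion.

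**Causality.** Section 10.1.2 has five grades. *Likely* joins three conditions: plausible timing, and that the event "abates upon discontinuation of the study product and cannot be reasonably explained by the known characteristics of the study participant's clinical state". The grade above it reads "Definitely: The AE follows a reasonable temporal sequence from the time of study product administration or reappears when study product is reintroduced".

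**What depends on these.** Section 10.1.2 states: "The causality assessment is one of the criteria used when determining regulatory reporting requirements". Section 10.3 sets the deadlines: "SUSARs which are fatal or life-threatening must be reported not later than 7 days after the sponsor is first aware of the reaction". Other SUSARs have 15 days.

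**The concern.** Expectedness should sort every adverse reaction into exactly one of two classes. The case that most needs a clear rule is a known reaction that turns out worse than the reference document describes. Under section 10.1.3 such a reaction is expected because its nature is listed, and unexpected because its severity is not. For a serious related reaction, that choice decides whether it is a SUSAR and whether a 7- or 15-day deadline applies. A reader who stops at the first bullet could treat it as expected and not expedite it.

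The causality scale has a separate ordering fault. Relatedness is recorded for every adverse event (section 6.5.3), and a graded scale is useful only if each step up asks for at least as much evidence as the step below.

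**Working it through.** The protocol gives no figure to reproduce here, so the check is logical. The definitions are laid out as written and every case is counted.

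**Expectedness.** Let N mean that the nature is consistent with the RSI, and S that the severity is consistent. Section 10.1.3 gives:
- *Expected* = N or S
- *Unexpected* = not N, or not S

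| Nature | Severity | Expected (10.1.3) | Unexpected (10.1.3) | Section 10, strict reading | Section 10, joint reading |
|---|---|---|---|---|---|
| consistent | consistent | yes | no | no | no |
| consistent | not | **yes** | **yes** | no | yes |
| not | consistent | **yes** | **yes** | no | yes |
| not | not | no | yes | yes | yes |

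*Expected* holds in 3 of 4 rows and *Unexpected* in 3 of 4. Two rows meet both (3 + 3 − 4 = 2). The third row is practically empty, because a reaction absent from the RSI has no listed severity to agree with. That leaves one live row: listed nature, greater severity.

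The section 10 wording can be read two ways. Read strictly, nature and severity must both be inconsistent, and only 1 row is unexpected. Read jointly, the reaction's overall profile fails to match, and 3 rows are unexpected, exactly as in the second bullet of 10.1.3. The overlap inside 10.1.3 is present under either reading.

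As an illustration, Appendix 4 section 1.2.1 lists herpes simplex, including eczema herpeticum, as common on abrocitinib. A case more severe than the SmPC describes would fall in row two. The SmPC text is not in the protocol, so whether a given case would exceed it cannot be checked.

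**Causality.** Take four yes/no conditions, which give 2⁴ = 16 combinations: timing (T), abatement on stopping (A), no explanation from clinical state (X) and reappearance on reintroduction (R).
- *Likely* = T and A and X, with R free: 2 combinations.
- *Definitely* = T or R: 16 − 4 (neither T nor R) = 12 combinations.
- Every *Likely* combination contains T, so both also meet *Definitely*. The remaining 12 − 2 = 10 meet *Definitely* without meeting *Likely*.

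Timing alone is therefore enough for the top grade. An event with plausible timing that the participant's condition could explain fits *Possible* and, literally, *Definitely* too.

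**Check of the repairs.** With *Expected* = N and S, *Expected* holds in 1 row and *Unexpected* in 3. The total is 4 and the overlap is 0. For causality, merely replacing the 'or' in *Definitely* with 'and' gives T and R, which is 4 combinations. Only 1 of them meets *Likely*, so 3 would still skip its conditions. Requiring T, A, X and R leaves 1 combination, nested inside *Likely*.

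**The case against.** Several points on the other side are sound.

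- **The sponsor's office still sees every serious event.** Section 10 sends all SAEs to the KHP-CTO within 24 hours, whatever their expectedness, for review under its pharmacovigilance policy. Section 10.3 makes that office responsible for SUSAR reports. A reader might infer that the wording lets a site withhold a serious event from the sponsor, but the protocol does not support that. The policy, which is not shown, may resolve the ambiguity in practice. It would not remove the overlap from the document that sites use.
- **Section 10 need not conflict with 10.1.3.** A reader might infer a flat contradiction from the 'and' in section 10. That depends on the strict reading of a definition the protocol attributes to regulation. The joint reading agrees with the *Unexpected* bullet.
- **The causality order does not by itself decide SUSAR status.** It is tempting to say that both faults do so. *Likely* and *Definitely* would ordinarily both count as related, so choosing between them changes nothing for reporting. The protocol does not say which grades count as an adverse reaction, so nothing stronger can be shown. Section 10.1.2 also tells the investigator to weigh alternative causes, which softens the literal reading of *Definitely*. It still directs the investigator to use grades that overlap.
- **Severity is not seriousness.** Section 10.1.1 separates the two, and section 10 lists death as a seriousness criterion. A fatal outcome should therefore not be taken automatically as severity beyond the RSI.
- **Comparability between arms.** A reader might infer that relatedness grades will differ by arm. All arms use the same text, no mechanism is stated, and the safety outcomes in section 4.2 are adverse events and events of special interest, not relatedness grades.

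None of this supplies a rule for a listed reaction of greater severity.

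**Conclusion.** The point holds for expectedness in section 10.1.3. A reaction of listed nature and greater than listed severity meets both definitions, and its SUSAR status, if it is serious and related, depends on which bullet is applied. The size is one live combination out of four. That counts categories, not events, and the protocol gives no basis for estimating how many reactions would be affected. The conclusion rests on the bullets as written and assumes no overriding rule in the unseen pharmacovigilance policy.

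The *Definitely* wording in section 10.1.2 is a real but separate and smaller fault: the top grade asks for less than the one below it. It affects the ordering of the recorded relatedness scale. No claim is made that it changes which events become SUSARs. No outcome, analysis or power figure is affected by either fault.

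**What to change.** 1. In section 10.1.3, define *Expected* as nature **and** severity both consistent with the RSI. Keep *Unexpected* as either one not consistent.
2. In section 10, leave the regulation-derived definition as it stands and add one sentence saying that it is to be read in the same way as section 10.1.3: a mismatch in either nature or severity makes the reaction unexpected.
3. In section 10.1.2, reword *Definitely* to require all the *Likely* conditions plus reappearance on reintroduction or equivalent confirmation. Swapping 'or' for 'and' in the present sentence is not enough, because it would not bring in abatement or the absence of another explanation.

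The cost is a short wording amendment and matching guidance on the SAE form. The downside is possibly a few more expedited reports. Sample size and analysis are unchanged.
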